## 4 Study Design

This is a multisite Phase I/II clinical trial of GTB-3550 (CD16/IL-15/CD33) tri-specific killer cell engager (TriKE) for the treatment of CD33-expressing high risk myelodysplastic syndromes, refractory/relapsed acute myeloid leukemia or advanced systemic mastocytosis. Up to 10 study centers may take part in this trial.

Patients receive a single course of GTB-3550 TriKE given as 3 weekly treatment blocks. Each block consists of four consecutive 24 hour continuous infusions of GTB-3550 TriKE followed by a 72 hour break after Block #1 and #2. All treatment is given as an inpatient.

Toxicities are monitored through Day 28 (as assessed on Day 29) with continued toxicity assessment through Day 60. Disease response is assessed by bone marrow biopsy performed between Day 21 and 42 after the start of the 1st infusion. Follow-up for response and survival continues through 6 months from study treatment start.

The study consists of two components. The dose finding component is a modified version of a Phase I trial and the extended component is a modified Phase II trial.

**Dose Finding Component:** The Phase I component uses a continual reassessment method (CRM) to determine the maximum tolerated dose (MTD) of GTB-3550 TriKE. Up to 7 doses levels will be tested. The goal of the CRM is to identify the dose level which most closely corresponds to the targeted dose limiting toxicity (DLT) rate of 20%.

Patients are enrolled in cohorts of 2 beginning at Dose Level 1. A minimum of 1 week must separate each patient. Both patients within a cohort must reach Day 28 (end of the DLT assessment period) prior to enrollment of a subsequent cohort. The study statistician assigns each new cohort of 2 patients to the most appropriate dose level based on updated toxicity probabilities. As enrollment proceeds, each cohort is assigned to an increased, decreased or equivalent dose level based on prior data in the trial until the study sample reaches 30. At this time, the last dose is declared the MTD and the GTB-3550 TriKE dose for the extended component.

**Extended Component:** The primary goal of the extended component is to study the potential efficacy of GTB-3550 TriKE in this patient population. Efficacy is measured using rates of complete and partial remission. A Simon's MiniMax two-stage design is used in this phase. Monitoring guidelines are in place to stop the study early for excessive toxicity.

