## 8.1 Required Standard of Care

Standard of care procedures should be followed for all enrolled patients, including those who are enrolled for retreatment.

Activity	Screening within 30 days of enrollment (within 14 days if for eligibility)	Day 1, Day 8, and Day 15 (start of treatment block)	Daily during infusions (i.e. Day 2-5, 9 12, 16-19)	Day 22	Day 29	Anytime between Day 21 through Day 42	End of Treatment Visit Day 60 (±7 days)	FU for overall survival (through Month 6)
consent	X							
baseline assessment	X							
medical history	X	X		X	X		X	
concomitant meds 	X	X	X	X	X		X	
physical exam	X	X		X	X		X	
vital signs including pulse oximetry	X	X	per Section 7.1.1	X	X		X	
neurologic assessment		X 		X				
provider assessment			X					
survival status							X 	X
assessment of toxicity		X	X	X	X		X	
Karnofsky PS	X				X		X	
height	X							
weight		X (- 5 days)						
CBC/diff/plt	X	X	X	X	X		X	
basic metabolic panel			X					
comprehensive metabolic panel  , magnesium and phosphorus	X	X		X	X		X	
ALT, AST, total bili, albumin 			2 times					
hepatitis B and C screening	X							
INR 	X							
eGFR	X							
Serum pregnancy test for FOCBP within 7 days of treatment start	X							
Disease assessment	X					X		
BM biopsy 	X					X		
Electrocardiogram	X							
Echocardiogram, cardiac MRI or MUGA	X							
Chest/abdomen CT	X							
assessment of response						X		X 

1 - sample to TTL per [Section 8.2](#) at time of each SOC bone marrow biopsy

2 - Neurological assessment daily including basic motor (gait), coordination (steadiness) and cognitive function (alert and oriented) - any abnormalities should be followed up with a detailed neurologic exam.

3 - Albumin, alkaline phosphatase, ALT, AST, bilirubin (total), calcium, chloride, CO2, creatinine, glucose, potassium, protein (total), sodium, urea nitrogen

4 - perform LFTs and albumin twice more during infusion week (in addition to Day of infusion start CMP) = three times during infusion week

5 - survival status at Day 60 for early study stopping rule for expansion component only

6 - until relapse/progression or start of a new therapy, then survival only

7 - document all concomitant medications, including start and stop dates, relative to administration of GTB-3550 TriKE

8- Measure and report prior to commencement of GTB-3550 therapy for information only and not as criteria for inclusion.

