## 8.2 Research Related Testing, Assessments, and Sample Collections

Sample collections and other procedures after the end of the infusions will coincide with outpatient clinic visits which may not occur on the targeted day.

	Screen/ Baseline	Pre Dose 1 each Block (Day 1, 8, 15)	Daily during infusions (i.e. Day 2-5, 9-12, 16- 19)	PK/PD sampling at end of each infusion block	Day 22	Day 29	Day of SOC Disease Reassessmen t (Day 21 – Day 42)		
Toxicity Assessment			Refer to Section 10.2 for details						
Assessment for dose limiting toxicity			By Day 29 – report as DLT for Phase I only; however any patient experiencing a DLT is not eligible to continue treatment per Section 7.5						
Assessment for stopping rules			Expansion component only through Day 42 for non-hematologic, non-relapse, non- infectious toxicity (except fever), Day 60 for TRM,						
Monitoring for signs of immune activation			Pre and during TriKE infusions – all patients						
CRP, ferritin 	X	X	X (Day 5 only)						
Pulmonary Function Testing	X								
EKG		X (At 4 hours (±15 min) into the infusion)	X (at 4 hours (±15 min) into each daily infusion and at 4 hours (±15 min) after disconnect at block end)						
T Cell Subset Extended Profile 	X								
5 - 10 ml green top tubes and 1- 10 ml red top tube	X	X	X (Day 3, 10, and 17, only) 		X	X	X 		
antibody testing (sample obtained from the 10 ml red top collected in previous row)	X 	X (Day 15 only)			X	X	X 		
5 ml red top for each PK/PD time point		X	X	X 					
30 ml or as much as able to obtain of heparinized bone marrow aspirate at time of SOC bm bx	X 						X 		
Pre- and Post-TriKE drug product concentrations levels samples – each drug bag during Week 1 only									
TriKE pre-infusion sample - 2 ml of drug split between two pre- labeled 1.8 ml cryo-vials		Each drug bag during Week 1 only per Section 9.6 – collected after drug preparation is complete and before bag sent to floor, – keep refrigerated until pick-up							
TriKE post-infusion sample collection ~2 ml of drug split between two pre-labeled 1.8 ml cryo- vials		Each drug bag during Week 1 only – per Section 7.1 after infusion end and prior to discarding bag and tubing - keep refrigerated until samples are collected							

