## 10.2 Event Documentation

Event monitoring and documentation begins with the 1st dose of TriKEs.

For the purposes of this study, selected expected adverse events will be assessed using the Targeted Toxicity Worksheet ([Appendix VI](#)) and any unexpected events will be collected at the following time points in relation to the GTB-3550 TriKE infusions through Day 29:

- Prior to the infusion start of each 24 hour infusion (i.e. Day 1, 2, 3, 4, and Day 8, 9, 10, 11, and Day 15, 16, 17, 18)
- At the end of the final infusion of each block (i.e. Day 5, Day 12, Day 19)
- Day 22
- Day 29

At each time point, the worst grade of the targeted toxicity since the last assessment or the previous 24 hours (whichever is shorter) will be recorded in addition to any unexpected toxicities felt at least possibly related the study treatment.

If a patient discontinues study therapy early or otherwise does not receive treatment as planned, the targeted toxicity assessment time points may be adjusted or eliminated; however, patients must be assessed for a minimum of 28 days from the 1st dose of study drug.

If a patient is not abiding by the standard of care study calendar ([Section 8.1](#)), collection of the corresponding targeted events (and research related samples) also may be altered or discontinued on an individual patient basis, as appropriate.

Monitoring for adverse events will end after the last targeted assessment; however, the investigator is obligated, upon knowledge of, to report any event meeting the criteria in [Section 10.5](#).

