#### **10.4 Early Study Stopping Rules - Event Documentation and Reporting (Phase II Dose Expansion)**

Early study stopping rules for the Phase II dose expansion component patients are:

- Grade 4-5 non-hematologic, non-relapse, non-infectious toxicity (except fever) by 42 days after the start of the first GTB-3550 TriKE treatment block
- Non-relapse, non-infectious treatment related mortality (TRM) within 60 days of starting GTB-3550 TriKE treatment

Meeting either stopping rule criterion temporarily will halt study enrollment until the event is fully evaluated and the Principal Investigator and GT Biopharma make a decision regarding the continuation of the trial. Any patients currently receiving treatment may continue after discussion with the study PI and GT Biopharma.

Events that count toward dose limiting toxicity and early stopping rules do not necessarily constitute a serious adverse event requiring expedited reporting and should be reported as such only if they meet the criteria for expedited reporting as defined in [Section 10.6](#).

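### The 24-hour look-back in Section 10.2 leaves 288 of 672 hours ungraded on the targeted worksheet, and its Day 29 end of monitoring conflicts with Sections 4 and 8.1 and leaves Days 30–42 of stopping rule 1 with no stated collection method

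*Combined protocol and SAP*

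**What the plan says.** Section 10.2 lists the time points for the Targeted Toxicity Worksheet (Appendix VI): before each 24-hour infusion, at the end of each block, and on Days 22 and 29. At each one, "the worst grade of the targeted toxicity since the last assessment or the previous 24 hours (whichever is shorter) will be recorded". Unexpected toxicities thought at least possibly related are collected as well.

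The same section then says: "Monitoring for adverse events will end after the last targeted assessment". The last targeted assessment is Day 29. The only stated exception is that "the investigator is obligated, upon knowledge of, to report any event meeting the criteria in" Section 10.5, which deals with deaths.

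Other sections run longer:

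- Section 4 monitors toxicity through Day 28, "with continued toxicity assessment through Day 60".
- The Section 8.1 calendar has a row for "assessment of toxicity". It is marked at block starts, daily during infusions, on Days 22 and 29 and at the Day 60 visit. It is blank in the Day 21–42 column.
- Section 8.2 has a stopping-rule assessment row: "Expansion component only through Day 42 for non-hematologic" toxicity, and Day 60 for treatment-related mortality.
- Section 10.4 counts Grade 4–5 toxicity as a Phase II stopping event if it occurs "by 42 days after the start of the first GTB-3550 TriKE treatment block". Section 12.4 uses the same window.

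Section 12.1 makes toxicity through Day 29 a secondary endpoint, and Section 12.2 summarises safety by frequencies and proportions.

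**The concern.** There are two separate problems.

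First, the cap costs nothing on infusion days, when assessments are about 24 hours apart. It bites only in the breaks between blocks and in the week before Day 29. A targeted toxicity that starts and resolves there, more than 24 hours before the next assessment, has no place on the worksheet. If the worksheet feeds the Day 29 toxicity summary, brief non-serious events from those days can be missing from the reported frequencies.

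Second, a site cannot both end adverse-event monitoring at Day 29 and continue toxicity assessment to Day 60. The conflict matters for stopping rule 1, whose window runs about two weeks past Day 29. The mortality rule has its own Day 60 survival check (Section 8.1, footnote 5). The toxicity rule has no comparable step after Day 29.

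**Working it through.** **The plan's own figures.** The protocol gives no coverage figure. The nearest are the stopping probabilities in Section 12.4 for the boundary 2/3, 3/8, 4/13, 5/20, 6/26 or 7 events in 27 patients. Take an exact recursion over patients n = 1 to 27, with boundary b(n) = 2 for n ≤ 3, 3 for n ≤ 8, 4 for n ≤ 13, 5 for n ≤ 20, 6 for n ≤ 26 and 7 at n = 27. At each n, P(n, k) = P(n−1, k)(1−p) + P(n−1, k−1)p for k < b(n), and the probability reaching b(n) is counted as stopped. This gives 9.7% at a true rate of 10% (stated: at most 10%) and 87.8% at 30% (stated: 88%). Both agree. They assume that every qualifying event to Day 42 is captured.

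**Look-back coverage.** The time points from Section 10.2 are Days 1–5, 8–12, 15–19, 22 and 29, which makes 17. The window is 28 × 24 = 672 hours. For each consecutive pair, uncovered hours = gap − min(gap, 24).

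| Interval | Gap (h) | Covered (h) | Uncovered (h) |
|---|---|---|---|
| Consecutive infusion days | 24 | 24 | 0 |
| Day 5 to 8 | 72 | 24 | 48 |
| Day 12 to 15 | 72 | 24 | 48 |
| Day 19 to 22 | 72 | 24 | 48 |
| Day 22 to 29 | 168 | 24 | 144 |

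Total = 48 + 48 + 48 + 144 = 288 hours; 288/672 = 42.9%, or 12 of 28 days. With the ±1-day visit window of Section 8, moving Day 22 leaves the total unchanged. Moving Day 29 gives 264 of 648 to 312 of 696 hours. Without the cap, the uncovered time is 0 of 672 hours.

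**What could fall wholly inside a gap.** A Grade 3 event counts as dose-limiting only if it lasts more than 72 hours, apart from the listed exceptions (Section 7.2.1). A 48-hour gap cannot contain such an event; only the 144-hour gap can.

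**Stopping-rule window after Day 29.** 42 − 29 = 13 days, or 13/42 = 31% of the window. If 42 days after the start is read as Day 43, it is 14/42 = 33%. In this period Section 10.2 offers only reporting on knowledge, Section 8.1 has no toxicity visit before the end-of-treatment visit, and the Section 8.2 row names no visit or method.

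**Which events are exposed.** Appendix VI lists 15 items, of which 10 have a Grade 4 definition. Eight of the 10 are worded as life-threatening, so they would normally meet the serious definition in Section 10.1 and be reported within 24 hours of knowledge (Section 10.6). The other two are fever, which rule 1 excludes, and rash.

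**Can the end-of-treatment visit do the work?** It is at Day 60 ± 7 after three blocks. Otherwise it is about 6 weeks ± 1 week from the start of the last block (Section 7.6). If Block 1 was the last: Day 1 + 42 ± 7 = Days 36–50. If Block 2 was the last: Day 8 + 42 ± 7 = Days 43–57. So only patients who stop after Block 1, or who start a new treatment early, can have that visit before Day 42.

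**The case against.** The best defence is that the worksheet is one channel among several. It covers 15 expected items. Unexpected related toxicities are collected without a clear 24-hour limit, the Section 8.1 toxicity assessments on Days 8, 15, 22 and 29 carry no cap, and dose-limiting, serious and stopping-rule events have their own forms. No section makes the worksheet the sole source for the toxicity endpoint, and the case report forms are not in the documents. All of that stands, and it is why the first part is a gap in recording. A reader might infer that 43% of the dose-limiting-toxicity window goes unobserved, or that such toxicities are lost. The documents do not support that.

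A reader might also infer that the whole Day 42 window lacks active monitoring. It does not. Days 1–29 are covered, Section 8.2 names an assessment through Day 42, and the Day 60 toxicity assessment could pick up later events in retrospect. What remains is that, for about Days 30–42, nothing says how or when the events are to be collected.

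Nor does this show the stated 88% to be wrong. It reproduces, and the documents give no share of missed events from which a lower figure could be derived.

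It is fair, too, that a longer look-back only partly repairs the record. Fever, hypoxia and hypertension depend on measurements, and Days 22–28 would rest largely on recall.

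Finally, the pointer to Section 10.5 is clerical. Sections 10.6 and 10.7 impose reporting in their own right, and Section 10.4 already treats events as expedited "only if they meet the criteria for expedited reporting as defined in" Section 10.6. Reporting duties do not lapse because of it.

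**Conclusion.** Both parts hold in limited form, and both should be fixed.

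The look-back leaves 288 of 672 hours (43%), all off-infusion, without a worst grade on the targeted worksheet. The figure assumes assessments at the nominal times. Its effect on the Day 29 toxicity frequencies depends on how far they draw on the worksheet, which the documents do not say.

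The end-of-monitoring sentence in Section 10.2 agrees with the Day 29 endpoint in Section 12.1 but contradicts Section 4 and the Day 60 mark in Section 8.1. It leaves about Days 30–42 of stopping rule 1 without a collection method. The exposure is small: non-fatal Grade 4 events that the site does not learn of, or does not judge serious and so may not recognise as reportable once monitoring has ended. Rash and laboratory values are examples. Day 60 treatment-related mortality is not affected.

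**What to change.** 1. In Section 10.2, drop the 24-hour alternative, so that each assessment records the worst grade since the previous one. The cost is a wording change to the protocol and worksheet, slightly more data entry, and longer recall at existing visits.
2. Reconcile the end-of-monitoring sentence with Sections 4, 8.1, 8.2, 10.4 and 12.4. State that worksheet assessments end at Day 29, but that Grade 4–5 non-hematologic events with onset through Day 42 are collected, with onset dates, at the existing end-of-treatment toxicity assessment. If that visit falls before Day 42, collect them by record review or contact through Day 42. Section 7.6 already uses record review for survival.

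The second change needs no new visit or procedure, only a record check or contact for the few patients with an early end-of-treatment visit. Retrospective capture can lag by up to about 38 days (Day 29 to Day 67, the end of the visit window). At the stated 1–2 patients per month that is 38/30.4 = 1.25 months, or about 1.25 to 2.5 further enrolments. Events known to the site would still be reported within 24 hours.

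As an editorial correction, point the references to Section 10.5 in Sections 10.1 and 10.2 to Sections 10.6 and 10.7.

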### **10.3 Dose Limiting Toxicity Documentation and Reporting (Phase I Dose Finding)**

The following events count toward dose limiting toxicity (DLT) during the Phase I dose finding component and must be reported the UMN Multisite Program Manager per [Section 10.6](#).

Note: DLT events are only reported for patients enrolled in the Phase I portion of the trial; however, any patient experiencing a DLT is not eligible to continue treatment per [Section 7.5](#).

A DLT is defined as a related treatment emergent toxicity that occurs within 28 days after the 1st TriKE dose with the exception of those that are clearly and incontrovertibly due to extraneous causes:

- Any Grade 4 or 5 non-hematologic events
- Grade 3 non-hematologic adverse events lasting more than 72 hours, **except** the following:
  - Non-sustained (< 7 days) Grade 3 liver function tests (ALT/AST, alkaline phosphatase, total or direct bilirubin) abnormalities in the absence of clinical signs of hepatic dysfunction (lethargy, confusion, anorexia, pruritus or tremors).
  - Non-sustained Grade 3 QTc prolongation (< 72 hours) in the absence of cardiac arrhythmia
  - Grade 3 electrolyte disturbances that resolve, with or without intervention, to < Grade 2 levels within 72 hours
  - Grade 3 fatigue
  - Grade 3 anorexia
  - Grade 3 fever
  - Grade 3 infection
- Hematologic Toxicity - Given that AML and MDS inherently leads to low neutrophils and platelets, standard grading cannot be used as many of these patients technically meet criteria for “grade 4” neutropenia or thrombocytopenia at baseline. Thus, the hematologic DLTs are listed below:
  - AML
    - Grade 4 neutrophil count (< 500/ $\mu$ L) lasting  $\geq$  29 days from start of cycle in absence of evidence of active leukemia

- Grade 4 platelet count (< 25,000/ $\mu$ L) lasting  $\geq$  29 days from start of cycle in absence of evidence of active leukemia
- Any clinically significant bleeding that is not controllable with transfusion support
- MDS/mast cell diseases:
  - Grade 4 neutrophil count (<500/ $\mu$ L) lasting  $\geq$  29 days from start of cycle in absence of evidence of active MDS/mast cell disease
  - Grade 4 platelet count (<25,000/ $\mu$ L) lasting  $\geq$  29 days from start of cycle in the absence of active MDS/Mast cell disease
  - Any clinically significant bleeding that is not controllable with transfusion support
  - Grade 4 anemia, unexplained by the underlying disease
- Grade 3 infusion related, treatment related reaction including cytokine release syndrome which does not resolve within 72 hours despite best medical management (refer to [Section 10](#) for modified CRS grading)
- Grade 3 or 4 Tumor Lysis Syndrome that does not resolve within 7 days with or without intervention
- Inability to complete at least one block of three 24 hour infusions due to any treatment emergent, treatment related toxicity.

#### **10.4 Early Study Stopping Rules - Event Documentation and Reporting (Phase II Dose Expansion)**

Early study stopping rules for the Phase II dose expansion component patients are:

- Grade 4-5 non-hematologic, non-relapse, non-infectious toxicity (except fever) by 42 days after the start of the first GTB-3550 TriKE treatment block
- Non-relapse, non-infectious treatment related mortality (TRM) within 60 days of starting GTB-3550 TriKE treatment

Meeting either stopping rule criterion temporarily will halt study enrollment until the event is fully evaluated and the Principal Investigator and GT Biopharma make a decision regarding the continuation of the trial. Any patients currently receiving treatment may continue after discussion with the study PI and GT Biopharma.

Events that count toward dose limiting toxicity and early stopping rules do not necessarily constitute a serious adverse event requiring expedited reporting and should be reported as such only if they meet the criteria for expedited reporting as defined in [Section 10.6](#).

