		
 
Renumber references deleting references removed in July 2018 revision
 
 
Previous edits July 10, 2019 version Based on SIV:
 
 
Section 5.3, Appendices 1 and 2: clarify HIV status as "known history of HIV"
 
Section 7.1 and Section 7.3.2: replace references to hypersensitivity and allergic/anaphylactic with infusion related reaction as the study switched to CTCAE v 5 in the April 2018 protocol version – makes consistent with DLT definition and Appendix VIII Targeted Toxicity Worksheet use of infusion related reaction
 
Synopsis, Section 4 and Section 10.2 Update wording on Dose Limiting Toxicities (DLT) to 
 
Resolve discrepancies in wording found in the protocol and to clarify hematologic parameters for toxicity given the baseline hematologic abnormalities inherent to AML and MDS:
 
Updated hematologic toxicity parameters as the standard grading system does not apply to AML and MDS patients given their baseline platelets/neutrophils already meet grade 3 and 4 due to the disease process itself.
 
Added Grade 3 Infection to the exclusions for DLT given that infection is inherent in MDS/AML as a disease related complication
 
 
 
Section 9.6, 5th bullet final product samples: delete the words "to be handed to the infusion team member along with the infusion bag and tubing" to make consistent with rest of language in bullet and Section 8.2 as left over wording from a previous revision
 
Updated Appendix I and II to new CTO format for eligibility checklists
 
	
3	09/23/2019	
Throughout protocol: Replace the product name 161533 TriKEs with GTB-3550 TriKE™
 
Appendices I and II: Delete Eligibility Checklists per new CTO policy and renumber remaining appendices
	Update product name

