7	04/10/2020	
Section 7.4 and Section 8 – add language to clarify that the standard of care procedures in Section 8.1 should be followed for patients who are enrolled for retreatment.
 
Section 8.1 – clarified timing of procedures on the days of infusion.
 
Consent changes – added background information to retreatment consent and updated long term specimen storage language to state that samples will be under the control of GT BioPharma.
	Yes
8	05/18/2020	Study Schema, Section 7.2, and Section 10.3 – DLT assessments are protocol defined at Day 29. We recognized that our currently approved protocol has 2 different dates for assessment in the DLT section (Day 29 for non-hematologic and Day 42 for Hematologic assessment) which is incongruent. Thus, revised DLT assessments to clarify that hematological toxicity will be defined as lasting $\geq$ 29 days from start of cycle as all DLT assessments need to have the same timeline to be congruent with moving forward with subsequent patients at 29 days..	No
9	08/31/2020	
Section 7.1.5 and Section 7.5 – clarify that if after completing Block 1 and Block 2 patients with clear evidence of disease progression will discontinue treatment but will be fully evaluable for toxicity and efficacy
 
Section 7.1 and Section 9.6 – Update the drug preparation instructions to match the study's Pharmacy Manual
 
Section 12.1 – add the definition of evaluable and when to replace a patient to complete enrollment.
 
Other minor edits and clarifications
	No
10	10/05/2020	
Synopsis, Section 6.4 and Section 7.4 - clarify when re-treatment may be considered.
 
Section 10.6 – Delete [REDACTED] from the list of persons who receive participating sites event reports for initial review.
 
Section 10.7 – Clarify UMN's reporting flow to GTB and [REDACTED] for SAEs, remove link for MCC SAE reporting as process has changed and receiving report notification via [REDACTED].
 
Section 11.3 – Clarify that this study complies with the Masonic Cancer Data and Safety Monitoring Plan (DSMP) and add the link to the plan.
 
Section 11.5 – add ICH compliant record retention information.
 
Other minor edits and clarifications.
	No

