**Monitoring for Safety (Phase II Extended):**

- Grade 4-5 non-hematologic, non-relapse, non-infectious toxicity (except fever) by 42 days after the start of the first GTB-3550 TriKE treatment block
- Non-relapse, non-infectious treatment related mortality within 60 days of the 1st dose of GTB-3550 TriKE

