## **10.5 Documentation of Death and Reporting Requirements**

Deaths during treatment and the follow-up period, including death due to disease, will be recorded as an SAE and reported per [Section 10.6](#). Deaths due to disease should be recorded as a Grade 5 Neoplasm.

In addition, even after the follow-up period ends, the death date must be documented in the patient follow-up tab in [REDACTED] upon knowledge using the comment field in survival status section to record the cause.

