## 10.7 UMN Required Reporting: UMN IRB, GT Biopharma, [REDACTED], and Masonic Cancer Center's SAE Coordinator

Entity Reported To:	Criteria for reporting	Timeframe	Form to Use	Report to
U OF MN IRB	Information that indicates a new or increased risk, or safety issue. Unexpected Death per UMN requirements.	5 business days	Ethos Reportable New Information (RNI)	Via [REDACTED] with copy GT Biopharma*
	Clinical deviations per current IRB reporting requirements (UMN patients only)		[REDACTED] Deviation Report and [REDACTED]	
GT Biopharma and [REDACTED]*	Any event meeting the definition of serious regardless of attribution	Within 24 hours of knowledge	CTO SAE Report Form	GT Biopharma and [REDACTED]
	Events that count toward dose limiting toxicity during the dose finding component or an early study stopping rule during the expanded component	At time of reporting	Appropriate form	

\*GT Biopharma/[REDACTED] is responsible for submission of IND safety reports to the FDA per federal regulations.

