#### **11.4 UMN Led Teleconferences – Participating Sites, GT Biopharma** [REDACTED]

[REDACTED] Regular teleconferences will be held to facilitate communication between the participating sites and IND sponsor/representative regarding the study's progress, including patient updates, a summary of safety reports, dose level/patient slot availability, case report form completion, and other issues for discussion. The Masonic Cancer Center Multisite Program Manager is responsible for arranging these teleconferences and preparing the agenda. Meetings occur every 2 weeks; however, they may be scheduled more or less frequently at the discretion of the lead institution. Participation of a minimum of one representative from each participating clinical site is expected. Attendance by [REDACTED] GT Biopharma is agenda driven.

These teleconferences are in addition to other previously described site interactions including centralized patient registration, institutional and MCC required reporting of safety related issues, and case report form completion in the study's central database [REDACTED]

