## **12.4 Monitoring Guidelines (Study Stopping Rule Events)**

During the CRM, the trial will stop if the posterior probability that the lowest dose is more toxic than the target is greater than 90%.

After the MTD has been established stopping rules will also be employed to monitor excess toxicity outside of the Phase I trial.

Meeting either stopping rule criteria temporarily will halt enrollment per [Section 10.4](#).

**(1) Grade 4-5 non-hematologic, non-relapse, non-infectious toxicity (except fever) by 42 days after the start of the first GTB-3550 TriKE treatment block:** We will construct a boundary such that the probability of early stopping is at most 10% if the toxicity rate is equal to 10%. Assuming 27 additional patients are enrolled after phase I, the upper stopping boundary for toxicity would be 2/3, 3/8, 4/13, 5/20, 6/26 or 7 events.

**(2) Non-relapse, non-infectious treatment related mortality** within 60 days of starting GTB-3550 TriKE treatment: Assuming the same parameters as in (1), the upper stopping boundary for TRM will be 2/3, 3/8, 4/13, 5/20, 6/26 or 7 events. If the true rates of both toxicity and TRM are 30%, the probability of early stopping will be 88% for each guideline.

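### The Phase II mortality rule never counts an infectious death, even one attributed to GTB-3550; counting those judged probably or definitely related would be a cheap improvement

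*Combined protocol and SAP*

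**What the plan says.** The Phase II extension has two safety stopping rules. Rule (2), on mortality, is worded in Section 10.4 as "Non-relapse, non-infectious treatment related mortality (TRM) within 60 days of starting GTB-3550 TriKE treatment". The schema, under Monitoring for Safety, has "Non-relapse, non-infectious treatment related mortality within 60 days", and Section 12.4 repeats the restriction. Rule (1) covers Grade 4-5 toxicity by Day 42 and is also confined to non-infectious events.

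Section 12.4 sets the boundary for both rules at 2/3, 3/8, 4/13, 5/20, 6/26 or 7 events. It assumes 27 patients enrolled after Phase I and requires at most a 10% chance of stopping when the true rate is 10%. It adds: "If the true rates of both toxicity and TRM are 30%, the probability of early stopping will be 88% for each guideline". Under Section 10.4, meeting a rule pauses enrollment until the Principal Investigator and the sponsor decide whether to continue.

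Phase I is different. Sections 7.2.1 and 10.3 make any related Grade 4 or 5 non-hematologic event within 28 days a dose limiting toxicity (DLT). Infection is exempted only at Grade 3, and the Revision History gives the reason: "Added Grade 3 Infection to the exclusions for DLT given that infection is inherent in MDS/AML as a disease related complication".

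Deaths are captured in any case. Section 10.5 says: "Deaths during treatment and the follow-up period, including death due to disease, will be recorded as an SAE".

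**The concern.** Rule (2) already asks whether a death is treatment related. It then discards the death if the mechanism was infection, however firm the attribution. The only reason the documents give for setting infection aside concerns background infection in MDS and AML, and it was given for Grade 3 infection in the DLT definition. That reason does not reach a death that has been judged drug-caused.

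Section 12.1 says the extension is meant to confirm safety at the MTD. At stake is whether a cluster of drug-attributed infectious deaths would trigger a pause through a number fixed in advance, or only through someone acting on individual reports.

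**Working it through.** **1. What each rule counts.** Take a fatal infection judged definitely related to GTB-3550.

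| Where | Window | Counted? | Reason |
|---|---|---|---|
| Phase I DLT (7.2.1, 10.3) | 28 days | Yes | Grade 5 non-hematologic; only Grade 3 infection is exempt |
| Phase II rule (1) (10.4, 12.4) | 42 days | No | limited to non-infectious events |
| Phase II rule (2) (schema, 10.4, 12.4) | 60 days | No | limited to non-infectious deaths |

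The DLT list places infection among the exceptions to the non-hematologic Grade 3 criterion, so the protocol itself treats infection as non-hematologic.

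**2. Effect on the count, with no assumed rate.** If all the deaths are infectious and drug-attributed, 2 in the first 3 patients, 3 in the first 8, or 7 in 27 each give a rule (2) count of 0. Each would meet the boundary if counted.

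**3. Reproducing the plan's figures.** Let p be the probability that a patient has a counted death, and let k(n) be the halting count at patient n: 2 for n ≤ 3, 3 for n ≤ 8, 4 for n ≤ 13, 5 for n ≤ 20, 6 for n ≤ 26, then 7. With a(n, e) the probability of e counted deaths after n patients and no halt so far,

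a(n, e) = a(n−1, e)(1−p) + a(n−1, e−1)p.

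At each n, the probability with e ≥ k(n) is moved to the halted total. The first step can be done by hand. The chance of at least 2 in 3 is 3p²(1−p) + p³, which is 0.027 + 0.001 = 0.028 at p = 0.10 and 0.189 + 0.027 = 0.216 at p = 0.30. Carried through 27 patients:

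- p = 0.10: 0.0973, against a stated limit of 10%
- p = 0.30: 0.8776, against a stated 88%

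Both reproduce. They describe non-infectious deaths only, because those are the only deaths counted.

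**4. Counting probable or definite infectious deaths.** Let p₀ be the non-infectious treatment-related death rate and q the rate of infectious deaths judged probable or definite. As written, the counted rate is p₀; under the fix it is p₀ + q, with the boundary unchanged. The documents give no value for q, so 1%, 2% and 5% are assumptions. With 27 patients:

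| p₀ | As written | q = 1% | q = 2% | q = 5% |
|---|---|---|---|---|
| 5% | 1.4% | 2.3% | 3.6% | 9.7% |
| 10% | 9.7% | 12.7% | 16.0% | 28.3% |

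Section 12.3 expects about 44 patients in total, which leaves 44 − 30 = 14 after Phase I. With 14 patients the p₀ = 5% row is 1.3%, then 2.0%, 2.9% and 6.8%. The p₀ = 10% row is 6.8%, then 8.6%, 10.6% and 17.6%.

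**5. What happens to the design figures.** If the 10% reference rate is taken to cover all counted deaths (p₀ + q), the recursion is unchanged: 9.7% at a total of 10% and 87.8% at 30%. Neither the boundary nor the sample size has to move.

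**The case against.** The strongest reply is that the exclusion is a deliberate choice, worded alike in three places, and that these deaths are already seen. Section 10.7 sends the sponsor, within 24 hours, "Any event meeting the definition of serious regardless of attribution". Section 10.6 sets the same 24 hours for participating sites, with forwarding to the sponsor within 3 business hours. Section 11.4 provides teleconferences, normally every two weeks, covering "patient updates, a summary of safety reports". The Revision History says the study complies with the cancer center's data and safety monitoring plan, the abbreviation list includes a Data and Safety Monitoring Council, and part of Section 11.3 is redacted. A trigger for deaths may exist there. Section 7.1.5 also bars a new block while there are signs of infection. A halt, moreover, only hands the decision to people who already receive the reports.

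Most of this stands. A reader might infer that drug-caused infectious deaths go unmonitored, or that the 88% is miscalculated. The documents support neither: reporting is prompt, and the figure is right for the defined event. What remains is narrower. In the visible text, no pre-specified count includes these deaths.

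It is also fair to say that the size of the gain depends on an assumed rate. At the 1% end it is small, and many patients are neutropenic at baseline, so a probable or definite attribution may be uncommon. Finally, how much mortality to tolerate before pausing is the sponsor's decision, and keeping the boundary while widening the event lowers that tolerance.

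**Conclusion.** The point holds as a cheap improvement to a safety rule. An infectious death attributed to GTB-3550 reaches neither Phase II boundary, while the same death within 28 days in Phase I would be a DLT.

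The count-based consequence is certain: three such deaths in the first 8 patients score 0 where the boundary is 3. The probabilities are illustrative. They rest on assumed rates, on 27 patients as in Section 12.4, and on independent patients with a constant risk. Whether the redacted monitoring plan already covers the gap cannot be determined.

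A reader might take the exclusion for an oversight. Its consistent wording suggests intent, though no reason is given for Phase II. Nor would the fix bring full parity with the Phase I definition: Grade 4 infections, and fatal infections rated only possible, would stay uncounted. Sections 10.4 and 12.4 also do not name the attribution categories that make a non-infectious death treatment related. That is a separate missing detail, and its effect on halting has not been calculated.

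**What to change.** In the schema, Section 10.4 and Section 12.4, add to rule (2): *an infectious death counts if its relationship to GTB-3550 is probable or definite (Section 10.1)*. Keep the 2/3, 3/8, 4/13, 5/20, 6/26, 7 boundary. State that its 10% reference rate now covers all counted non-relapse treatment-related deaths. Leave rule (1) and the handling of non-infectious deaths as they are. The probable-or-definite threshold is meant to keep background infection out, in line with the reason given for the Grade 3 exception.

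The drafting cost is one sentence in three places plus the statement on the reference rate. Day 60 survival status (Section 8.1), reporting of deaths (10.5), the Stopping Rule Event Form (10.6) and the attribution scale (10.1) already exist.

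The operating cost is more temporary halts once total counted mortality exceeds 10%: with 27 patients, 28.3% at a total of 15%, against 9.7% at 10%. If the sponsor finds that too many, it can recalibrate the boundary.
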